8.2 Primary Efficacy Endpoint

The primary efficacy variables (as assessed by the CANTAB) are as follows:

- RVP mean response latency - defined as the mean response latency during assessment sequence blocks where the subject responded correctly (milliseconds).

BOMARIN [®]	SAP BMN165-303 Final Version 1.0	Page 14
-----------------------------	----------------------------------	---------

- SWM between errors 4-8 boxes – defined as the total number of times the subject revisits a box in which a token has previously been found in the same problem (calculated for assessed problems only).
- SST stop signal reaction time – defined as the length of time between the go stimulus and the stop stimulus at which the subject is able to successfully inhibit their response on 50% of trials.

The primary efficacy endpoints are change from baseline in these variables at Part 2 Week 8.

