### 9.5.1 Primary Efficacy Variable

The primary efficacy variables (as assessed by the CANTAB) are as follows:

- RVP mean latency
  - RVP mean latency is the mean response latency during assessment sequence blocks where the subject responded correctly (milliseconds).
- SWM between errors
  - SWM between errors measures the total number of times the subject revisits a box in which a token has previously been found in the same problem (calculated for assessed problems only).
- SST stop signal delay
  - SST stop signal delay is the length of time between the go stimulus and the stop stimulus at which the subject is able to successfully inhibit their response on 50% of trials.

The primary efficacy endpoints are these variables collected in Part 2, Week 8.

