### **14.3 Primary Efficacy Analysis**

No multiplicity adjustment will be performed for multiple primary efficacy endpoints. Each primary efficacy endpoint will be compared between High Active Group (Study 165-302) and the pooled Placebo Groups (Study 165-302) and between the Low Active Group (Study 165-302) and the pooled Placebo Groups (Study 165-302) using Analysis of Covariance Model (ANCOVA) with treatment and baseline assessment as factors. For this study, baseline is defined as the assessment collected during the Part 2, Day 1 visit (predose) of Study 165-302.

The primary efficacy endpoints will also be summarized descriptively over time in Part 4 at Week 9, Week 25, and Week 49.

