4.2 Treatment Group Presentation

When analyzing data collected while subjects are in Part 2 of Study 165-302, the following treatment groups will be used for presentation:

- Pooled active group
- Pooled placebo group

When analyzing data collected while subjects are in Part 4 of Study 165-302, all subjects will be combined and an overall summary will be provided.

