8.2.1 Primary Analysis Method

Descriptive summaries will be presented for the primary efficacy endpoints.

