8.2.2 Secondary Analysis Method

Descriptive summaries will also be present for data collected in Part 4 for the primary efficacy variables at each scheduled visit.

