8.4 Exploratory Efficacy Endpoint

8.4.1 Stop Signal Task

SST (as assessed by the CANTAB) related endpoints will be summarized based on the following assessments:

Proprietary and Confidential

B.OMARIN[®]	SAP BMN165-303 Final Version 1.0	Page 15
-----------------------------	----------------------------------	---------

Descriptive summaries will be presented for each variable at each visit. Change from baseline will be presented as well. These results will also be listed.

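### The SAP changes the primary endpoint from Week 8 value to change from baseline and drops the baseline-adjusted ANCOVA, so the active-placebo difference read from its summaries carries chance baseline imbalance and is less precise

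*SAP*

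**What the plan says.** Protocol 9.5.1, and the synopsis in the same terms, fixes the endpoint as the observed value: "The primary efficacy endpoints are these variables collected in Part 2, Week 8". Protocol 14.3 compares each active dose group with pooled placebo "using Analysis of Covariance Model (ANCOVA) with treatment and baseline assessment as factors".

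SAP 8.2 redefines the endpoint: "The primary efficacy endpoints are change from baseline in these variables at Part 2 Week 8". It neither mentions nor explains the difference from the protocol. SAP 8.3 defines the secondary endpoints as change in the same way.

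The whole of SAP 8.2.1 reads: "Descriptive summaries will be presented for the primary efficacy endpoints". Section 8.3.1 repeats that sentence, including the word primary, under the secondary endpoints. SAP 4.2 sets the Part 2 columns as "Pooled active group" and its placebo counterpart, and combines all subjects in Part 4. The SAP contains no ANCOVA, test or between-arm estimate.

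The exploratory endpoints are described more fully. SAP 8.4.1 plans summaries of each SST variable at every visit and adds: "Change from baseline will be presented as well". Protocol 14.7 and SAP 3 both state that the SAP takes precedence over conflicting statistical text, without an amendment.

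The SST primary measure is also named differently in the two documents. That is a separate matter, and the algebra below holds for either measure.

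**The concern.** Moving from a Week 8 value to change from baseline is usually harmless, because a model containing baseline returns the same treatment effect for both. Here the model went at the same time as the endpoint was redefined. What remains is a mean change in each of two columns, and a reader who wants the treatment effect will subtract one from the other.

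That subtraction removes the full baseline difference between arms, whereas ANCOVA removes only the part that predicts the Week 8 score. Whenever the within-arm slope is below 1, the simple difference in change over-corrects for chance baseline imbalance, and it has a larger standard error.

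This matters because Part 2 Week 8 is the only post-baseline time at which the SAP shows active and placebo separately. The substudy plans about 100 subjects, so a chance imbalance in at least one cognitive score would not be unusual, and there is little precision to spare. The baseline needed for adjustment is already collected in the substudy.

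**Working it through.** **No figure to reproduce.** The sample-size sections show no SD, effect size or power in the published text, so results are in units of the between-subject SD.

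**Inputs**
- About 100 subjects (SAP 3.2).
- 2:1 active to placebo within each dose (SAP 3.5.2), so about 67 versus 33 when pooled. Assumed: the parent-study ratio carries over to the substudy and all subjects are evaluable.
- Assumed: equal SD at baseline and Week 8, and a correlation r of 0.3, 0.5 or 0.7 between them. With equal SDs, the within-arm slope b equals r.

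**Identities.** Let dY and dB be the arm differences in means at Week 8 and baseline.
- ANCOVA on the value: dY − b·dB.
- ANCOVA on change: the slope becomes b − 1, so the estimate is (dY − dB) − (b − 1)·dB = dY − b·dB. This equals the previous line.
- Unadjusted change: dY − dB.
- Unadjusted change minus ANCOVA: −(1 − b)·dB.

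Randomisation gives dB mean zero, so the gap has mean zero. The groups are held fixed as pooled active and pooled placebo. The SAP's pooling of the two doses is a further departure from the protocol that this calculation does not cover.

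**Numbers**
- SE(dB) = √(1/67 + 1/33) = 0.213 SD.
- SD of the gap = (1 − r) × 0.213.
- SE of unadjusted change = 0.213 × √(2(1 − r)).
- SE of ANCOVA = 0.213 × √(1 − r²).
- Variance ratio, change to ANCOVA = 2(1 − r)/(1 − r²) = 2/(1 + r).

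| r | SD of gap | SE, unadjusted change | SE, ANCOVA | Variance ratio |
|---|---|---|---|---|
| 0.3 | 0.149 | 0.252 | 0.203 | 1.54 |
| 0.5 | 0.106 | 0.213 | 0.184 | 1.33 |
| 0.7 | 0.064 | 0.165 | 0.152 | 1.18 |

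A chance baseline difference larger than 0.2 SD in either direction has probability 0.35 for each variable. At exactly 0.2 SD, the change difference departs from ANCOVA by 0.14, 0.10 and 0.06 SD at the three correlations.

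**Check by simulation.** In 4,000 trials of 67 versus 33 at each of r = 0.5 and 0.7, with a true effect of 0.30 SD, ANCOVA on value and ANCOVA on change agreed to within 1.4 × 10⁻¹⁵. The gap had SD 0.108 and 0.066, close to the formula. Mean estimates were 0.309 (change) and 0.308 (ANCOVA) at r = 0.5, and 0.301 for both at r = 0.7, which confirms that there is no bias.

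**The case against.** The strongest reply is that the SAP plans no contrast, so none can be wrong, and that the precedence rule settles which definition applies. Both statements are true. The first limits the point to the difference that a reader forms from the two columns. But those columns are the only post-baseline treatment information in the substudy, and the protocol had promised an adjusted comparison. The second settles which text governs, but it does not supply the missing adjustment.

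Three stronger readings are tempting, and the documents do not support them.

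- **That redefining the endpoint itself changes the treatment effect.** A reader might set the unadjusted Week 8 difference against the unadjusted change difference. The two differ by dB, with SD 0.213 and a probability of 0.35 of exceeding 0.2 SD. Neither document plans an unadjusted Week 8 contrast. Against the protocol's own model, with the groups held fixed, the gap exceeds 0.2 SD with probability of only about 0.18, 0.06 and 0.002 for each variable at r = 0.3, 0.5 and 0.7.
- **That the protocol's endpoint is not summarised at all.** SAP 4.5 commits to summarising every efficacy measure by study week, with Part 2 windows for baseline and Week 8. Section 8.2.1 is only less explicit than 8.4.1.
- **That Part 2 and Part 4 are reported on different scales.** This rests on 8.2.1 speaking of endpoints while 8.2.2 says "Descriptive summaries will also be present for data collected in Part 4 for the primary efficacy variables at each scheduled visit". Neither section rules out the other quantity.

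**Conclusion.** The point holds as one about lost adjustment. The SAP replaces a baseline-adjusted comparison with unadjusted summaries of change, and does not explain the new endpoint definition. The consequence is noise, not bias: a mean-zero departure from the ANCOVA estimate with SD of about 0.15, 0.11 or 0.06 SD, and a variance 1.54, 1.33 or 1.18 times as large, at correlations of 0.3, 0.5 and 0.7. At r = 0.5, adjustment lowers the standard error from 0.213 to 0.184 SD.

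These sizes rest on 67 versus 33 evaluable subjects, equal SDs at the two visits and the assumed correlations. The documents give none of these for the substudy beyond the planned total and the parent-study ratio. If the correlation is high the loss is small: at r = 0.9 the gap has SD 0.021 and the standard errors are 0.095 and 0.093 SD. The direction does not depend on r: in large samples with equal SDs, the adjusted estimate is the more precise one at any correlation below 1.

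**What to change.** 1. In SAP 8.2.1 and 8.3.1, report the Part 2 Week 8 active-versus-placebo difference for each variable as an ANCOVA estimate with baseline as covariate and a confidence interval. Correct the reference to primary endpoints in 8.3.1. Fitted to the same subjects, the estimate is identical for value and change, so the choice of definition stops affecting the comparison.
2. In the same sections, state that observed baseline and Week 8 values are shown next to change, as 8.4.1 does. Given SAP 4.5, this is clarification. Use the subjects with both measurements, since SAP 4.7 does not impute missing data and both change and ANCOVA need both visits.
3. In SAP 8.2 and 8.3, note that the endpoint definition differs from the protocol and give the reason.

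The cost is one simple model per variable in an otherwise descriptive SAP, a few table rows and some wording. No new data, visits or subjects are needed.

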8.2.1 Primary Analysis Method

Descriptive summaries will be presented for the primary efficacy endpoints.

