### **14.4 Secondary Efficacy Analysis**

Each secondary efficacy endpoint will be analyzed similar to the primary efficacy endpoints.

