3 INTRODUCTION

Study BMN 165-303 is a Phase 3 substudy to BMN 165-302 to evaluate executive function in adults with phenylketonuria (PKU) who are participating in the pegvaliase Phase 3 Study, 165-302. The purpose of this Statistical Analysis Plan (SAP) is to provide a comprehensive description of methods of the data analyses outlined in the protocol (dated April 08, 2015).

If discrepancies exist between the text of the statistical analysis as planned in the protocol and the final SAP, a protocol amendment will not be issued and the SAP will prevail.

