3.1 Objectives of Study

The primary objective of this study is to evaluate executive function in adult subjects with PKU who are participating in Study 165-302, as measured by selected Cambridge Neuropsychological Test Automated Battery (CANTAB) tasks.

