4 GENERAL ANALYSIS CONSIDERATION

Descriptive summaries of continuous variables will include the mean, standard deviation (SD), median, and range for the mean. Descriptive summaries of categorical variables will include n and percent.

The baseline value of an assessment is defined as the available measurement collected on Day 1 of Part 2 of Study 165-302, unless otherwise specified.

Data from Study 165-302 will be integrated in combination with data in this study when necessary for efficacy analysis.

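### The SAP replaces the protocol's baseline-adjusted comparison with placebo by within-arm descriptive summaries, so no active-placebo difference or confidence interval is planned at Part 2 Week 8 (minor)

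*SAP*

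**What the plan says.** Protocol 14.3 compares the High Active and the Low Active group, each against the pooled placebo groups, "using Analysis of Covariance Model (ANCOVA) with treatment and baseline assessment as factors". Protocol 14.4 carries this over: "Each secondary efficacy endpoint will be analyzed similar to the primary efficacy endpoints". Protocol 9.5.1 and 9.5.2 place both sets of endpoints at Part 2 Week 8.

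SAP 8.2 and 8.3 keep the Week 8 time point and define the endpoints as change from baseline. The analysis method in SAP 8.2.1 is one sentence: "Descriptive summaries will be presented for the primary efficacy endpoints". SAP 8.3.1 repeats that sentence under the secondary endpoints. SAP 4 gives the content of a summary: "Descriptive summaries of continuous variables will include the mean, standard deviation (SD), median, and range for the mean". SAP 4.2 sets the arms: "When analyzing data collected while subjects are in Part 2 of Study 165-302, the following treatment groups will be used for presentation", followed by a pooled active and a pooled placebo group.

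On precedence, SAP 3 says that if the documents differ, "a protocol amendment will not be issued and the SAP will prevail"; Protocol 14.7 says the same. The objective in SAP 3.1 reads "The primary objective of this study is to evaluate executive function in adult subjects with PKU".

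**The concern.** Week 8 is the only scheduled post-baseline visit at which randomisation supports a comparison. All subjects receive pegvaliase in Part 4 (Protocol 9.1, SAP 3.2), and SAP 4.2 then combines them into one group. The protocol's only comparative analysis sits at this visit, and it has no counterpart in the visible SAP. The SAP contains no between-group difference, no interval for one, no baseline adjustment and no dose-specific presentation.

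At stake is how the Week 8 results can be read. Two columns of means and SDs invite the reader to compare the arms by eye without a stated uncertainty. A baseline-adjusted difference cannot be recovered from such a table, because it needs the within-subject association between baseline and Week 8.

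**Working it through.** **Text comparison**

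| Element | Protocol 14.3, 14.4 | SAP 4, 4.2, 8.2.1, 8.3.1 |
|---|---|---|
| Method | ANCOVA | Descriptive summaries |
| Active arms | High and Low, separately | Pooled |
| Control | Pooled placebo | Pooled placebo |
| Baseline | Covariate | Subtracted (change score) |
| Between-group estimate | Yes | None stated |

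The range for the mean in SAP 4 is unclear wording. Even if it is read as an interval, it describes one arm, not a difference between arms.

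**Size of what is lost**

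The documents show no SD, correlation or effect size for the CANTAB variables, and the text under both sample-size headings (Protocol 14.6, SAP 3.4) is not visible. There is therefore no stated figure to reproduce, and the following is an illustration.

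Inputs:
- N of about 100 is the planned enrolment (SAP 3.2).
- The 67:33 split follows from 2:1 randomisation at both dose levels (SAP 3.5.2): 100 × 2/3 ≈ 67.
- Assumed: correlation ρ between baseline and Week 8 of 0.3, 0.5 or 0.8; complete, normal data; equal variance at both visits.
- Unit: between-subject SD at one visit.

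Formulas for the 95% half-width:
- Crude difference in change: t(0.975, N−2) × √[2(1−ρ)(1/n₁ + 1/n₂)]
- Baseline-adjusted: t(0.975, N−3) × √[(1−ρ²)(1/n₁ + 1/n₂)]

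For 67:33, 1/67 + 1/33 = 0.0452, with square root 0.2127. The t values are 1.984 (98 df) and 1.985 (97 df).

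| ρ | Crude | Adjusted | Narrower by |
|---|---|---|---|
| 0.3 | 1.984 × 0.2127 × √1.4 = 0.499 | 1.985 × 0.2127 × √0.91 = 0.403 | 19% |
| 0.5 | 1.984 × 0.2127 × √1.0 = 0.422 | 1.985 × 0.2127 × √0.75 = 0.366 | 13% |
| 0.8 | 1.984 × 0.2127 × √0.4 = 0.267 | 1.985 × 0.2127 × √0.36 = 0.253 | 5% |

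For a smaller sample, assumed 20:10 with ρ = 0.5, √(1/20 + 1/10) = 0.387. The crude half-width is 2.048 × 0.387 × 1 = 0.79 SD and the adjusted one is 2.052 × 0.387 × √0.75 = 0.69 SD.

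The protocol's dose-specific contrasts, with about 33 against 33 and 96 df, would have adjusted half-widths of 0.47, 0.42 and 0.29 SD at the three correlations.

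The adjusted formula ignores chance baseline imbalance between arms. That matters little at 100 subjects but does matter in very small arms. In simulated normal data that include it, at ρ = 0.8 with 5 subjects per arm, the mean half-width was 0.93 SD adjusted and 0.89 SD crude. At ρ = 0.9 with 10:5 it was 0.53 against 0.52 SD.

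**The case against.** The strongest reply is that this is a governed change and not a defect. Both documents let the SAP override the protocol without an amendment. The objective is to evaluate executive function and names no comparison. The substudy gives no drug and does no randomisation of its own, and the SAP plans no test. Choosing description over inference is defensible in that setting. This stands, and it is why the point is minor. The precedence rule settles which text governs, but it does not supply an estimate.

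A second reply is that the sample may be small. SAP 4.3 declines site adjustment on that ground, and SAP 3.2 gives the enrolment of about 100 as what had been planned. Neither passage is offered as the reason for dropping the ANCOVA, and a reason may sit in text that is not visible. But both suggest that the 67:33 figures may be optimistic. With fewer subjects both intervals are wide, which is a reason to state the uncertainty.

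A third reply is that a reader can compute the crude difference and its interval from arm means, SDs and group sizes. This is correct, provided that the evaluable number is shown; SAP 4 does not list n for continuous variables. The adjusted estimate remains out of reach.

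A reader might infer more than the documents support:
- That the documents are in unresolved conflict. They are not, because the precedence rule resolves it.
- That the plan would let a practice effect pass as benefit. The placebo arm is shown beside the active arm, so a gain common to both would be visible, and Protocol Table 9.1.1 schedules a practice session before baseline.
- That the ANCOVA is the best estimate these data can give. No other estimator was compared, and in very small arms with high correlation it can be slightly less precise than the crude difference.

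**Conclusion.** The point holds, at minor severity. The governing plan gives no between-group difference, interval or baseline-adjusted estimate at Week 8 for any of the six primary and secondary CANTAB variables. It also drops the two dose-specific contrasts, and no visible text gives a reason. No false claim follows.

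The avoidable loss is a stated interval, plus a precision gain of 5% to 19% at the planned size. That gain rests on the assumed correlations, complete data and a 67:33 split. The text comparison needs no assumption.

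**What to change.** In SAP 8.2.1 and 8.3.1, for each of the six CANTAB variables, add beside the descriptive table the pooled active minus pooled placebo difference in Week 8 change, adjusted by ANCOVA for the Part 2 baseline, with its 95% confidence interval. Use subjects with both assessments, in line with SAP 4.7 (no imputation), and show their number per arm. With baseline in the model, the treatment difference is the same for the Week 8 value as for change, so the protocol's and the SAP's endpoint forms give one answer.

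Present the result as estimation only, with no significance claim and two notes:
- The six intervals are not adjusted for multiplicity. With no true effect and independent variables, the chance that at least one excludes zero is 1 − 0.95⁶ = 0.265.
- A complete-case interval does not reflect uncertainty from dropout.

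State that the dose-specific contrasts are dropped, or show them as supportive. I would not add a rule that switches to the crude difference below a set arm size: the simulated results depend on the split and on an unknown correlation, and give no clear cut-off.

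As an editorial correction, make SAP 8.3.1 and 8.3.2 name the secondary endpoints and variables; both now name the primary ones.

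The cost is SAP wording and one model per variable on data already collected. The intervals will be wide if few subjects are evaluable, and in very small arms with high correlation the adjusted interval can be slightly wider than the crude one. Supportive dose contrasts would add twelve intervals (six variables × two doses).

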8.2.2 Secondary Analysis Method

Descriptive summaries will also be present for data collected in Part 4 for the primary efficacy variables at each scheduled visit.

8.3 Secondary Efficacy Analysis Endpoint

The secondary efficacy variables (as assessed by the CANTAB) are as follows:

- RVP A prime (A') – defined as the signal detection measure of sensitivity to the target, regardless of response tendency (the expected range is 0.00 to 1.00; bad to good).
- SWM strategy 6-8 boxes – defined as the number of distinct boxes used by the subject to begin a new search for a token (within the same problem). Calculated for assessed problems with six boxes or more.
- SST proportion of successful stops – defined as the proportion of completed stop trials that were successful stops.

The secondary efficacy endpoints are the change from Baseline in these variables at Part 2 Week 8.

8.3.1 Primary Analysis Method

Descriptive summaries will be presented for the primary efficacy endpoints.

8.3.2 Secondary Analysis Method

Descriptive summaries will also be present for data collected in Part 4 for the primary efficacy variables at each scheduled visit.

8.4 Exploratory Efficacy Endpoint

8.4.1 Stop Signal Task

SST (as assessed by the CANTAB) related endpoints will be summarized based on the following assessments:

Proprietary and Confidential

B.OMARIN[®]	SAP BMN165-303 Final Version 1.0	Page 15
-----------------------------	----------------------------------	---------

Descriptive summaries will be presented for each variable at each visit. Change from baseline will be presented as well. These results will also be listed.

